9.7.5 Management of adverse reactions/events

After vaccination, grade 1 or grade 2 adverse reactions, such as redness, swelling, pain or (and) fever and general malaise etc. can disappear automatically, without any special treatment.

The investigators should conduct the investigation and follow-up on the adverse reactions/events occurred in the participants from the beginning of the immunization to day 28 after the second of the immunization, including medical history, physical examination and necessary laboratory examination, treatment and follow-up until the events are resolved.

9.7.6 Report serious adverse events

(1) Reporting Procedures for Investigators

The study institutions shall establish an emergency response plan for SAE handling. Upon learning of an SAE, regardless of whether it is related to the trial vaccine, the investigator must immediately (within 24 hours as required) fill out the Serious Adverse Event Report Form, send the initial report to the sponsor (via the dedicated pharmacovigilance email for clinical trials: [REDACTED]), and copy the report administrator. In case of emergency, the 24-hour emergency contact can also be reached [REDACTED]. Subsequent supplementary information/reports shall be submitted as soon as possible until the event is resolved.

When filling out the Serious Adverse Event Report Form, the investigator shall report the entire situation in writing, including but not limited to the name and relevant description of the adverse event, the occurrence time and type of the SAE, duration, severity, causal relationship with

vaccination, outcome, measures taken (symptomatic treatment), and other relevant clinical and laboratory data.

In case of a death event, the investigator shall report to the sponsor and the EC, and provide the autopsy report and final medical report.

Meanwhile, the clinical trial responsible institution/investigator shall promptly forward the sponsor's latest safety information reports on the clinical trial to the EC.

The EC shall receive SAE reports and other safety information reports, keep abreast of the occurrence and handling of SAEs throughout the clinical trial, and conduct follow-up reviews on the handling and reporting of SAEs during the trial.

(2) Reporting Procedures for the Sponsor

The day on which the sponsor first becomes aware of a valid report is designated as Day 0. After receiving the SAE reported by the investigator, the sponsor's pharmacovigilance personnel shall immediately review the completeness and accuracy of the original data. If necessary, they shall send inquiries to the investigator. At the same time, the sponsor shall analyze and evaluate the report, including the severity, relevance to the trial vaccine, and whether it is an unexpected event.

During the drug clinical trial, for adverse reactions determined to be SUSARs, the sponsor's pharmacovigilance personnel shall submit SUSAR reports to the national drug regulatory authorities and health authorities in accordance with the requirements of the Drug Registration Administration Measures ^[1], Good Clinical Practice ^[2], and Standards and Procedures for Rapid Reporting of Safety Data During Drug Clinical Trials ^[28]. If the investigator and the sponsor cannot reach an agreement on the causal relationship between the adverse event and the drug, and either party judges that the relationship with the investigational vaccine cannot be ruled out, the sponsor shall also submit a rapid report.

The sponsor shall submit SUSAR reports to all investigators, study institutions, and ethics committees participating in the clinical trial. Investigators shall promptly read the reports provided by the sponsor and submit the signed reports to the ethics committee.

For SUSAR that are non-fatal or non-life-threatening, the sponsor shall report them as soon as possible after first becoming aware, but no later than 15 calendar days; for unexpected serious adverse reactions that are fatal or life-threatening, the sponsor shall report them as soon as possible after first becoming aware, but no later than 7 calendar days, and submit and complete follow-up information within the subsequent 8 calendar days.

9.7.7 Grading of Adverse events

The solicited local adverse events and unsolicited systemic adverse events: The classification criteria for solicited adverse events are mainly referred to the “Guidelines for criteria classification for adverse events in clinical trials of prophylactic vaccines” ^[29] (2019) issued by NMPA, as shown in the table below. The solicited adverse events and unsolicited adverse events with the same symptoms are classified according to the following:

Table 11 Grading of local solicited adverse events

Grade 1	Grade 2	Grade 3	Grade 4
Tenderness (6-23 Resistance or	Crying upon contact	Persistent crying and	Requiring emergency

months old)	withdrawal upon contact or touch	or touch, but consolable	unconsolable	treatment or hospitalization
Pain (24-35 months old)	Not affect or slightly affect limb activity	Affect limb activity	Affect daily life	Loss of basic self-care ability, or hospitalization
Induration* #, Swelling#	$\geq 2.5\text{cm}$ in diameter and $<50\%$ of the vaccinated limb (anatomically the limb where the vaccinated site is located, e.g. upper arm or thigh) in area	$\geq 2.5\text{cm}$ in diameter and $<50\%$ of the vaccinated limb (anatomically the limb where the vaccinated site is located, e.g. upper arm or thigh) in area	$\geq 50\%$ of the vaccinated limb or ulcerated or secondary infection or phlebitis or wound drainage in area	Abscess, exfoliative dermatitis, dermal or deep tissue necrosis
Redness#, rash* #	$< 2.5\text{cm}$ in diameter	$\geq 2.5\text{cm}$ in diameter and $<50\%$ of the vaccinated limb (anatomically the limb where the vaccinated site is located, e.g. upper arm or thigh) in area	$\geq 50\%$ of the vaccinated limb or ulcerated or secondary infection or phlebitis or wound drainage in area	Abscess, exfoliative dermatitis, dermal or deep tissue necrosis
Pruritus	Pruritus at the vaccination site, but will be relieved without any treatment or within 48 hours after treatment	Pruritus at the vaccination site, and will not be relieved within 48 hours after treatment	Affect daily life	NA

* In addition to directly measuring the diameter of induration and rash for grading, the progress of the measurements should also be recorded.

The largest diameter or area of the induration, swelling, rash and redness should be measured; and the evaluation and grading should be based on the functional grade and actual measurement results, selecting the higher grading index.

Table 12 Grading of systemic solicited adverse events

	Grade 1	Grade 2	Grade 3	Grade 4
Acute allergic reaction*	Local urticaria (blister), treatment not required	Local urticaria (blister), treatment required; or mild angioedema, treatment not required	Generalized urticaria or angioedema, treatment required; or mild bronchospasm	Allergic shock, or Life-threatening bronchospasm, or laryngeal edema
Skin and mucosal abnormalities	Erythema/pruritus/color change	Diffuse Rashes/maculopapules/erythema/desquamation	Blistering/exudation/desquamation/ulcer	Exfoliative dermatitis involved mucosa, or erythema multiforme or suspected Stevens-Johnson syndrome
Diarrhea	Slight or transient, 3 ~ 4 times/day; abnormal fecal character, or slight diarrhea lasting shorter than 1 week	Mild or transient, 5~7 times/day; abnormal fecal character, or mild diarrhea lasting longer than 1 week	>7 times/day; abnormal fecal character, or bloody diarrhea, orthostatic hypotension or electrolyte imbalance, intravenous infusion >2L required	Hypotension and shock, hospitalization required
Anorexia	Appetite decreased, without food intake reduced	Appetite decreased, with food intake reduced, but without significant	Appetite decreased, with significant weight loss	Intervention required (eg. tube feeding and for

	Grade 1	Grade 2	Grade 3	Grade 4
		weight loss		parenteral nutrition)
Vomiting	1~2 times/24 hours, without affecting the movement	3~5 times/24 hours, or affect the movement	>6 times/24 hours, or intravenous infusion required	Hypotensive shock, hospitalization require, or other means of nutrition required
Nausea	Transient (< 24 hours), or Intermittent and with food intake generally normal	Persistent nausea leads to food intake reduced (24~48 hours)	Persistent nausea leads to food intake very little (> 48 hours), or intravenous infusion required	Life threatening (e.g. hypotensive shock)
Cough	Transient, no treatment required	Persistent cough, treatment effective	Paroxysmal cough, uncontrollable by treatment	Emergency treatment or hospitalization
Fatigue	Normal movement	Normal reduced movement	Severely affecting the movement and unable to work	Emergency treatment or hospitalization required
Irritability	Mild irritability	Irritable	Unsoothable	NA
Lethargy	Mild lethargy	Drowsiness	Hyporesponsiveness	NA
Vital signs-				
Fever, axillary temperature (°C)	37.5~<38.0	38.0~<39.5	≥39.5	≥39.5, for successively 5 days

*refers to hypersensitivity of Type I.

For the adverse events not included in the above grading tables, the severity of adverse events is to be graded according to the following grading criteria:

Mild (Grade 1): short duration (<48h) or slight discomfort, without affecting the movement and no treatment is required;

Moderate (Grade 2): Mild or moderate movement is limited, and medical attention might be required, but with no or only mild treatment;

Severe (Grade 3): Movement is limited significantly, requiring medical attention and treatment, and might require hospitalization; and

Critical (Grade 4): The critical illness can be life threatening, severely limiting the movement and requiring Intensive Care.

Grade 5: Death

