9.5 Safety follow-up observation

Observe the participants on-site for adverse events within 30 minutes after each dose of vaccination; and give the participants the diary cards after each dose to record the solicited adverse events (systemic and local) from day 0 to 7 after the vaccination and unsolicited adverse events from day 0 to 28 after the vaccination. Investigators will explain the judgment of adverse events, measurement methods, recording methods, precautions, reporting methods, etc., and distribute diary cards, rulers,

and thermometers. They will also train the participant's guardian on using the thermometer, observing adverse events, filling in the diary card, and make an appointment for the return time. Request the subject's guardian to fill out the diary card in detail from day 0 to 28 after the vaccination to record any clinical symptoms, medications and the use of other vaccines.

Conduct systematic observation 0-7 days after each dose of vaccination. The participant's guardian observes the subject's symptoms and signs every day and fill them in the diary cards for the investigators to collect safety observation data from day 0 to 7. From day 8 to 28, record the adverse events by using the method of voluntary reporting from subject's guardian and regular follow-up by investigators; and at day 28, take back the diary cards. Monitoring of SAEs and AESIs will continue until 6 months after the second of vaccination. SAEs and AESIs from day 29 after the second of vaccination to 6 months after the second will be collected through a combination of telephone follow-up once every 2 months and active reporting by the subject.

The participants should be informed of recording any adverse events at any time. In case of acute allergic reaction, Grade 3 or above adverse event or SAE, they should report to the investigators at any time and the investigators should conduct investigation, verification, and follow-up after learning until the event is resolved so as to finally complete the detailed investigation and follow-up records, which should include following:

- Description of adverse events
- Start time and end time of adverse events
- Severity classification of adverse events
- Correlation with the vaccination
- Laboratory results
- Treatment

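### Protocol Table 11 prints one criterion for both Grade 1 and Grade 2 induration/swelling, so the Grade 1/Grade 2 split for these two local events is incomplete or depends on the reader

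*Protocol*

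**What the plan says.** Protocol 9.7.7 grades solicited local events in Table 11 and solicited systemic events in Table 12.

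- **Induration and swelling (Table 11).** The Grade 1 cell and the Grade 2 cell both read "\geq 2.5\text{cm}$ in diameter and $<50\%$ of the vaccinated limb", followed by the same parenthesis explaining the limb. Grade 3 starts at 50% of the limb or at listed complications. Grade 4 is abscess, exfoliative dermatitis or necrosis.
- **Redness and rash (Table 11, next row).** Grades 2 to 4 carry the same text as the row above, but Grade 1 is "< 2.5\text{cm}$ in diameter".
- **Notes to Table 11.** The largest diameter or area of induration, swelling, rash and redness is to be measured. Grading is to be "based on the functional grade and actual measurement results, selecting the higher grading index".
- **Scope.** The lead-in says "The solicited adverse events and unsolicited adverse events with the same symptoms are classified according to the following", so the same row grades later-onset induration or swelling.
- **General scale.** The generic severity scale that closes 9.7.7 is introduced with "For the adverse events not included in the above grading tables".
- **Vomiting (Table 12).** The counts per 24 hours are 1 to 2 (Grade 1), 3 to 5 (Grade 2) and more than 6 (Grade 3). Effect on movement is an alternative route to Grade 2, and need for intravenous infusion an alternative route to Grade 3.

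SAP 6.9.1 tabulates adverse events by severity. When a subject has the same event more than once, it analyses the most severe occurrence. The SAP contains no grading criteria of its own.

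**The concern.** A grading scale should give every recorded reaction exactly one grade. The induration/swelling row fails twice below Grade 3: small reactions fit no cell, and mid-sized ones fit two. Small reactions can well be recorded, because under Protocol 9.5 the investigators "distribute diary cards, rulers" and thermometers to guardians.

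The SAP severity tables and the most-severe-event rule both need one grade per event. If the table was applied as printed, some induration and swelling events have no grade. Others are Grade 1 or Grade 2 depending on who graded them, and in a multi-center trial the readings can differ between sites. Severity is part of the plan's safety assessment: Protocol 9.7.2 bases it on the severity of local and systemic events. The rationale in 2.4 also cites work showing no increase in severity with the full dose.

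The vomiting gap is smaller. It is a single count value, but it lies between Grade 2 and Grade 3.

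**Working it through.** The plan gives no figure to reproduce. The check codes the printed cut-offs as rules and reads off the grade for example reactions.

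**Inputs (Protocol 9.7.7).**

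- Induration/swelling: Grade 1 and Grade 2 both require diameter ≥ 2.5 cm and area < 50% of the limb. Grade 3 requires area ≥ 50%.
- Redness/rash: Grade 1 is diameter < 2.5 cm. Grade 2 is ≥ 2.5 cm and < 50%. Grade 3 is ≥ 50%.

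The sizes below are illustrative and assume no complication such as ulceration or infection.

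| Diameter, share of limb | Induration/swelling as printed | Induration/swelling, note as tie-break | Redness/rash |
|---|---|---|---|
| 1 cm, 1% | none | none | 1 |
| 2.4 cm, 3% | none | none | 1 |
| 2.5 cm, 4% | 1 and 2 | 2 | 2 |
| 8 cm, 40% | 1 and 2 | 2 | 2 |
| 12 cm, 60% | 3 | 3 | 3 |

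The redness/rash row gives one grade each time. The induration/swelling row does so only from 50% of the limb upward.

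**Does other text repair the row?**

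- The note on the higher grade compares a functional grade with a measured one. The row prints no functional criterion at Grade 1 or 2, so the note has nothing to compare there. Stretched into a tie-break between columns, it settles the overlap as Grade 2, leaves Grade 1 unreachable, and does nothing below 2.5 cm.
- The general scale covers only events outside the tables. Induration and swelling are in the table.
- The SAP adds no criteria.

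**Vomiting (Table 12), count only.** Episodes 1 to 9 in 24 hours give grades 1, 1, 2, 2, 2, none, 3, 3, 3. Six episodes get a grade only if the movement, infusion or a Grade 4 criterion applies. Diarrhea in the same table is contiguous: 3 to 10 stools a day give 1, 1, 2, 2, 2, 3, 3, 3.

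**Reach.** Table 11 lists tenderness/pain, induration, swelling, redness, rash and pruritus. Two of these six are affected, at Grades 1 and 2 only.

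**The case against.** **A copying or extraction slip.** The text is a translation read from PDF, and parts of Table 11 are visibly broken. A duplicated cell, or a lost equals bar in the vomiting row, would be a one-cell or one-symbol error. That possibility stands and must be checked first. It is not shown, however: Grades 3 and 4 sit in the right columns, the neighbouring row keeps its own Grade 1, and the greater-or-equal sign survives elsewhere in both tables. A merged Grade 1/2 cell would leave the same ambiguity.

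**Unseen documents.** The protocol bases its criteria mainly on a national guideline and provides for eCRF completing guidelines and data queries. Any of these may hold a workable definition. This stands as a limit: nothing shows that any event was actually ungraded or graded inconsistently.

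**Low consequence.** No safety endpoint in Protocol 7.2 is defined by grade, and all arms share the table. This also stands and keeps the point modest.

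Four stronger readings are tempting and are not supported.

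- A reader might infer that the Grade 1 and Grade 2 counts cannot be derived at all. Under the tie-break reading, every reaction from 2.5 cm to under 50% of the limb is Grade 2, and only the smaller ones lack a grade.
- A reader might infer that swelling cannot be re-graded, because the asterisked footnote, "In addition to directly measuring the diameter of induration and rash for grading", names only induration and rash. That footnote concerns recording progress over time. The other note requires the largest diameter or area of swelling as well.
- A reader might take the statement in SAP 6.9.1 that solicited events follow the protocol as a rule on grading. In context it concerns classifying them as local or systemic. The severity tables and the most-severe-event rule are what depend on grade.
- A reader might infer that the vomiting gap threatens trial suspension. The rule in Protocol 7.8 needs Grade 3 or above events in at least 15% of participants, or 0.15 × 3,300 = 495 if all participants are the denominator (an assumption, since none is stated). One count value could matter only very near that line, so the link is remote. The gap could in rare cases touch the instruction in 9.5 for prompt reporting ("Grade 3 or above adverse event or SAE, they should report to the investigators at any time") and the SAP's Grade 3 or above listing.

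**Conclusion.** The point holds in a bounded form. As printed, induration and swelling under 2.5 cm without a Grade 3 or 4 feature have no grade. Those of at least 2.5 cm and under 50% of the limb have two grades, or only Grade 2 if the note is used as a tie-break. The Grade 1/Grade 2 split for these two events, including unsolicited events with the same symptoms, is therefore incomplete or reader-dependent.

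For induration and swelling, overall incidence, Grade 3 or above counts and the suspension criteria are unaffected. Immunogenicity is unaffected. No direction of bias is claimed. The documents give no incidence or size distribution, so the number of children affected cannot be stated.

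The vomiting gap is a minor companion point that adds little weight.

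The conclusion assumes that the printed cells match the source-language protocol and that no site document replaced them.

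**What to change.** 1. Check the induration/swelling cells and the vomiting bins against the source PDF and the source-language protocol.
2. Reconcile the two induration/swelling cells with each other, the redness/rash row, the cited guideline, the diary card and the eCRF completing guidelines. Reconcile the vomiting bins in the same way. No cut-off is proposed here.
3. Confirm which definitions the sites applied.
4. Before the severity tables are produced, check or re-derive the affected grades. Use the largest diameter or area that Table 11 already requires for induration and swelling, and recorded vomiting counts where available.
5. If any event still has no grade after that, state in the SAP how it is displayed.

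The cost is low: a document check, one table row, one bin boundary, at most one SAP sentence, and a pass through measurements the protocol already calls for. No new data collection is needed.

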9.8 Concomitant medications and vaccines

9.8.1 Concomitant medications

(1) Upon the occurrence of adverse events during the trials, it is allowed to conduct some necessary treatments and medical treatments.

(2) When severe allergic reactions or life-threatening reactions occur, first aid measures should be taken immediately.

(3) The investigators should record the information about any drug combinations, including names, dosage forms, dosages and time of use, etc.

9.8.2 Concomitant vaccines

- (1) Other vaccines shall be administered at least 7 days after receiving the investigational vaccine.
- (2) During the trial when emergency vaccines are needed, the participants should get vaccinated, such as rabies and tetanus vaccine.
- (3) For concomitant vaccines, detailed information should be recorded, including their names, usages and time of the vaccination.

9.8.3 Record of Concomitant Medications and Vaccines

To understand and rule out the impact of concomitant medications and vaccines administered during the trial on the safety and immunogenicity of the trial vaccine, as well as to collect all possible adverse events that may be related to vaccination, investigators shall guide participants' guardians to record details of medical visits, concomitant medications, and vaccines in the diary card as much as possible. In the event of an SAE or AESI, the participant's guardian shall be contacted to assist in providing the corresponding medical records, and efforts shall be made to complete the information collection. If it is indeed impossible to collect the information, "unknown" shall be noted in the relevant section of the original records.

9.9 Immunogenicity evaluation

The immunogenicity endpoints are SCR, SPR, GMT and GMI of influenza HI antibody of each strain.

9.9.1 Definitions

SCR: The percentages of participants with either a pre-vaccination titer $<1:10$ and a post-vaccination titer $\geq 1:40$, or a pre-vaccination titer ≥ 10 and a ≥ 4 -fold increase in post-vaccination titer

Seroprotection: HI antibody titer is $\geq 1:40$.

9.9.2 Laboratory test method

Micro-hemagglutination inhibition test will be used to test the antibody.

9.10 Data management

9.10.1 Source Data

The source Data shall include the informed consent, diary cards and original records, etc., which record the following basic data:

- Name of the trial and participant number;
- Demographic data;
- Inclusion/exclusion criteria;
- Vaccination record;
- The date of the follow-up and the date the participants terminate the trials;
- Adverse events/reactions and their management and outcome;
- Concomitant medical treatment and other vaccinations;

All data should be recorded in source documents, which should be properly stored in a specialized space by the investigator. The original data should be archived at the study site, which is the basis of the participants' participation in the clinical trials and the true integrity of the data.

The investigators should keep the original records carefully, accurately and timely; and all the collected original data should be recorded on the same day. It is required to fill in the record with a black pen. Any errors should not be altered, but be underlined and fill in the correct next to it, and signed with name and the date.

